**REGIONAL DISTRIBUTION OF VENTILATION MONITORING:**

- PulmoVista monitoring and lung expansion therapy will occur only one time as described above. .
- The following information will be displayed on the PulmoVista 500 device’s main monitoring screen during lung expansion therapy, but study investigator staff administering therapy and study participants will be blinded from information displayed on the screen’s monitor during therapy session in an effort to reduce performance bias:

[figure not shown]
A: Dynamic imaging showing impedance changes in a caudo-cranial image referenced to a dynamic baseline.  
 B: Tidal image showing EELI during inspiration and exhalation of the last detected breath.  
 C: Global impedance waveform showing relative impedance changes across electrode plane.  
 D: Regional impedance waveforms  
 F: Tidal respiratory rate  
 G: Global tidal variation displayed as 100%.  
 H: Regional tidal variation displayed as a percentage of global tidal variation.  
 - Once lung expansion therapy

IRB-HSR # 19661: A descriptive observational pilot study comparing regional distribution of ventilation during lung expansion therapy in healthy human subjects

session has ended, the researcher will detach trunk cables from electrode cables, detach reference electrode snap from adhesive ECG electrode, unclamp the electrode belt, and then remove belt from the study subject. Subject participation in this study is considered complete at this time.

- Inspect of electrode belt contact area will be performed to assess for evidence of skin irritation or bruising. Study participant will be notified by study investigator at the time of skin assessment if significant skin irritation or bruising is present. Finding will be recorded by study investigator.

- Displaying changes
  - The following information will be displayed and used to record pre and post lung expansion therapy end-expiratory lung impedance changes:

- Electrode belt, patient cable, and PulmoVista 500 EIT device (Draeger; Lubeck, Germany) will be removed study participant’s room and returned to a storage location outside of patient care areas.
- Following each EIT to subject interface disconnect, an alcohol, aldehyde, or quaternary ammonium based compound will be soaked on a wipe cloth to disinfect the surfaces of the patient cable, electrode belt, trunk cable, and EIT unit.

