**► IF YES, describe the stratification/ randomization scheme.**

**INSTRUCTIONS:**

The stratification factors and/or the randomization plan should be identified. If there is no randomization component or important patient characteristics that will be used in treatment allocation or data analysis, a statement to this effect should be included.

Stratification factors: These are pretreatment patient characteristics which could be balanced across treatment arms by design or may be used to determine starting dose or treatment allocation.

If randomization is going to be used, the details of the randomization plan should be described.

The description should include:

- the method and timing of randomization
- the type of randomization scheme that will be used in the study
- whether or not the randomization masked/blinded/if so, then to whom is it masked/blinded
- who has access to the randomization scheme

**Answer/Response:** Parallel randomized controlled trial

A recruitment email will be sent to University of Virginia Medical Center employees who represent the target study population. A university of Virginia email distribution list will be used to mass email respiratory therapy and nursing staff working in adult ICU and surgical acute care patient wards. Word of mouth will also be used to heighten awareness about this study. Adult intensive care fellows will also be invited to participate.

The target population will be encouraged to notify a study investigator if they are interested in being screened for eligibility to participate in this study. The study PI and sub-investigators will be responsible for recruitment and enrollment.

A computer generated random numbers generator will be used to randomly assign study subjects into an I.S. or EzPAP® lung expansion therapy group after documentation of informed consent has been recorded. Randomization masking/blinding will not occur in this study. The lung expansion therapy medical device designs and their respective operational differences are impossible to conceal (See images below).

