**Answer/Response:**

The focus of this study is to use electrical impedance tomography (EIT) monitoring to determine if there is a difference in regional distribution of ventilation when comparing Incentive Spirometry (I.S.) to EzPAP® lung expansion therapy.

Baseline characteristics will be reported as:

- Sex (M/F): n (%)
- Age (years): m (SD)
- Weight (BMI): m (SD) or M (IQR) depending upon normality of data distribution
- Tobacco History: n (%); Never smoked, Current smoker; Former smoker
- Respiratory Related Comorbidities: n (%)

Baseline and post-lung expansion therapy dependent variable metrics will be reported as end-expiratory lung volume impedance (EELI) for each of the following ventilation regions of interest:

- Ventral (Level of measurement- continuous)
- Mid-ventral (Level of measurement- continuous)
- Mid-dorsal (Level of measurement- continuous)
- Dorsal (Level of measurement- continuous)

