**Monitoring sessions and Lung Expansion Therapy procedure**

- **Lung expansion therapies will occur as follows:**
  - Study participants will sit with their back against a reclining chair with backrest adjust to 45-degrees.
- Monitoring will be initiated after researcher performs PulmoVista 500 EIT device (Draeger; Lubeck, Germany) setup and calibration.
- Approximate monitoring/measurement duration is 15-minutes.

IRB-HSR # 19661: A descriptive observational pilot study comparing regional distribution of ventilation during lung expansion therapy in healthy human subjects

- Two study investigators will be present during Incentive Spirometry and monitoring session. One study investigator will assist with EIT interface application and provide instruct study participants on how to perform I.S. therapy properly. A second study investigator will perform EIT device set-up and monitoring only.

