**Answer/Response:** Each study investigator has/will receive PulmoVista 500 EIT device (Draeger; Lubeck, Germany) didactic and clinical simulation training on how to prepare study participants for monitoring (i.e., determining electrode belt and cable selection), how to properly calibrate and operate the device, and how interpret, record, and download data to a password encrypted storage drive. Respiratory Therapy study investigators are content

experts with I.S. and EzPAP® training as these are lung expansion therapy standards of practice used at the University of Virginia Medical Center.

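### The plan guards against performance bias but not against reading bias: nothing says who extracts EELI, by what rule, or without knowledge of the arm

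*Combined protocol and SAP*

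**What the plan says.** **Masking.** Statistical Considerations, question 1 (randomization scheme) states: "Randomization masking/blinding will not occur in this study". The reason given is that the devices' "operational differences are impossible to conceal". Under Regional Distribution of Ventilation Monitoring there is one partial measure: "study investigator staff administering therapy and study participants will be blinded from information displayed on the screen’s monitor during therapy session", described as "in an effort to reduce performance bias".

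**Who is in the room.** For the incentive spirometry (I.S.) arm, Monitoring Sessions and Lung Expansion Therapy Procedure says "Two study investigators will be present during Incentive Spirometry and monitoring session". One gives instruction and helps fit the belt. For the other it says: "A second study investigator will perform EIT device set-up and monitoring only". The EzPAP section gives a second investigator the same role.

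**Who handles the data.** Appendix: Unapproved Device Use, question 7, has every study investigator trained in "how interpret, record, and download data to a password encrypted storage drive". The monitoring section says that displayed information is used to record EELI changes before and after therapy. It does not name the recorder. Whatever followed that sentence is missing from the readable text.

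**The endpoint.** Statistical Considerations, questions 2 and 4, make regional EELI the dependent variable in four regions, reported at baseline and after therapy. The two procedure sections provide five minutes of resting breathing before therapy and five minutes after it, in both arms.

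**What is stored.** The risk table in the Data and Safety Monitoring Plan says that a study ID, assigned in order of enrolment, is entered into the device and that raw recordings go to an encrypted drive. Statistical Considerations, question 1, has the study investigators generate the randomization scheme.

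**The concern.** Hiding the screen stops the therapist and participant from adjusting effort to what they see. It does nothing about how the recording is later turned into a number. The reason given for not masking, that the devices look and work differently, applies to people at the session. It does not apply to someone reading a resting segment of a stored file.

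EELI is produced by a device, but a five-minute recording does not yield one value by itself. Someone has to decide which breaths count, where the window starts and ends, and what to do with poor signal. Poor signal is foreseeable: the signal-check table lets measurement go ahead with unstable skin contact while warning that quality may suffer. If these decisions are open and the reader knows the arm, small leanings can accumulate in one direction. The Risk/Benefit section describes EzPAP as a means of raising dorsal lung volume, so a directional expectation is available for at least one of the four regions. Any such bias would fall directly on the I.S.-versus-EzPAP contrast, which is the primary comparison in Statistical Considerations, question 4.

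**Working it through.** **Step 1. Set the provisions side by side.**

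| Source of bias | Provision in the readable text |
|---|---|
| Therapist or participant reacts to the EIT display | Screen hidden from both during therapy |
| Knowledge of the arm among people at the session | None; stated to be impossible |
| Knowledge of the arm when EELI is extracted | None |
| Free choice of breaths, window or rejected signal | No rule given |

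The last two rows are the gap.

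**Step 2. Could a reader be masked?** In the therapy part of the trace the arms differ: deep breaths with I.S., normal breaths with EzPAP. A reader who sees the full trace could tell the arm. The five-minute segments before and after therapy are resting breathing in both arms and need not reveal it. These are the segments that supply the baseline and post-therapy values. Masked reading is therefore feasible for those values, provided the therapy part is removed first.

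**Step 3. Is the study ID enough?** No. IDs follow enrolment order and the investigators generate the allocation sequence. Anyone who knows that sequence can map ID to arm, so a separate random code is needed.

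**Step 4. What would a shift do to the error rate?** The plan has no figure to reproduce: no power analysis was done and no reading variability is given.

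- Total 30 subjects (Subjects, question 1). No allocation ratio is stated; I assume an even split, *n* = 15 per arm, so df = 2 × 15 − 2 = 28.
- Two-sided threshold 0.0125, and the independent-samples *t*-test named for normally distributed data (Statistical Considerations, question 4). The critical value is *t*(0.99375; 28) = 2.669.
- Shift δ, in SDs of the analysed EELI value, that arm-aware reading adds to the difference between arms when there is no true difference. **Assumed**, not from the documents.
- Non-centrality λ = δ × √(*n*/2) = δ × √7.5 = 2.739 δ.
- Rejection probability = P(|T| > 2.669), where T is non-central *t* with 28 df and non-centrality λ.

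| δ (SD) | λ | False-positive rate per region |
|---|---|---|
| 0 | 0 | 1.25% |
| 0.05 | 0.137 | 1.3% |
| 0.1 | 0.274 | 1.6% |
| 0.25 | 0.685 | 3.3% |
| 0.5 | 1.369 | 11.5% |

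A stricter threshold does not remove this. A systematic shift moves the centre of the test statistic, which the choice of 0.0125 leaves untouched.

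**The case against.** **The documents do not show arm-aware reading taking place.** A reader might infer that the investigator running the monitor also records EELI, sees the device in use, and picks breaths live from the screen. The plan does not say so. That role is described as set-up and monitoring only, the recorder is not named, and training every investigator to record data does not mean that the session operator does it. Sight of the device follows only from being present with devices that cannot be hidden. Since raw files are stored, reading after the session may already be intended, and the missing display material might have shown how values are obtained. All of this stands. What remains is that masking is ruled out without an exception for a reader, and that no reader or rule is specified.

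**The no-masking sentence may be over-read.** It answers a form question about randomization. It is not a considered rejection of masked endpoint reading, and it should not be presented as one. That argues for narrowing the sentence; it does not supply the missing provision.

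**The main gap is the extraction rule.** A mean over all breaths in a preset window removes most of the discretion, whoever reads the file. This is largely right, and the rule is the more important half of the fix. Masking still protects what is left, chiefly decisions about rejecting signal.

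**The error rates describe assumptions.** A reader might take 11.5% as this trial's false-positive rate. It is not: at 0.05 or 0.1 SD the rate barely leaves 1.25%.

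**The stakes are modest.** This is a 30-person proof-of-concept study in healthy volunteers with a device-measured endpoint and two-sided hypotheses. That limits the weight of the point. It does not dispose of it, since the plan still tests hypotheses at a stated threshold.

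**Conclusion.** The point holds in this form: the plan's only masking measure addresses performance bias, and the readable text leaves open who extracts EELI and how. Baseline and post-therapy values *may* therefore be selected by someone who knows the arm. That is an unprotected route to bias, not evidence of bias.

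The size cannot be derived from the documents. Under an assumed even split and the planned *t*-test, the consequence runs from negligible (about 1.6% at 0.1 SD) to serious (about 11.5% at 0.5 SD), against 1.25% nominal. The change is worth making because it is cheap and uses recordings the study already keeps. It covers only the resting segments: values taken during therapy cannot readily be masked, because the breathing pattern reveals the arm.

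**What to change.** 1. **Extraction rule (Statistical Considerations, question 4, and Regional Distribution of Ventilation Monitoring).** Take baseline and post-therapy EELI from the stored raw file, as the mean end-expiratory value of all breaths in a window of each five-minute resting segment. Fix the window and the signal-rejection rule before the first reading.
2. **Masked reading.** Trim each file to the resting segments and relabel it with a random code that is not the enrolment-order ID. Have it read by an existing investigator who was not at that session and does not hold the allocation list. Join allocation to the data only after all readings are locked.
3. **Wording (Statistical Considerations, question 1).** Limit the no-masking statement to the delivery of therapy, and state that any values taken during therapy cannot be masked.
4. **Fallback.** The team size is not given. If no unexposed investigator is available, apply the fixed-window rule alone and report unmasked reading as a limitation.

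**Cost.** A small trimming and recoding step, and readings done after the session. The plan names a principal investigator and sub-investigators and uses two per session, so exchanging files within the team may suffice. There are no extra visits or procedures for participants.

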**2. List the procedures, in bullet form, that will be done for RESEARCH PURPOSES as stipulated in this protocol.**

**INSTRUCTIONS:**  
Examples: blood tests, EKG, x-rays, surveys, administration of investigational drug/device, randomization to one of two approved drugs  
**Do NOT list those procedures which are being ordered for clinical standard of care.**  
If ALL procedures are being done for the research study, simply write: ALL

Answer/Response: All

**3. Do you confirm that, except for blood draws through a peripheral site, that all invasive procedures will be performed by a licensed health care provider under the supervision of an MD?**

Answer/Response: N/A, no invasive procedures done for this study.

**4. Will you be using data/specimens in this study that were collected previously, with the use of a research consent form, from another research study?**

**Answer/Response:** No

**IF YES, will the data/specimens be used in this study without a new consent from the original donor?**

**Answer/Response:**

**IF YES, explain how the proposed use is consistent with the use planned in this study and submit a copy of the consent form used to collect the data/specimens.**

**INSTRUCTIONS:** If you are unable to locate the consent form, you must request a Waiver of Consent. Consult with IRB staff to determine additional sections to be added to this protocol.

**Answer/Response:**

**5. Will any of the procedures listed in item # 2 have the potential to identify an incidental finding? This includes ALL procedures, assessments and evaluations that are being done for RESEARCH PURPOSES that may or may not be considered investigational.**

**Examples:** MRI/CT/PET/CXR shows possible tumor, Blood collected and analyzed using an investigational assay, Blood tests show possibility of leukemia, Surveys which reveal depression/suicidal tendencies.

**Answer/Response:** No

▶ **IF YES, check one of the following two options:**

The examination(s) utilize(s) the same techniques, equipment, etc., that would be used if the subject were to have the examination(s) performed for clinical care. **There exists the potential for the discovery of clinically significant incidental findings.**

- The PI takes full responsibility for the identification of incidental findings:
- The PI will inform the subjects verbally of all incidental findings that are of clinical significance or are of questionable significance.
- A follow-up letter describing the finding should be provided to the subject with instructions to either show the letter to their PC or if the subject has no PCP, the subject should be instructed to make an appointment at UVa or at the Free Clinic.

This examination(s) utilizes non-standard/investigational, technique, equipment, etc. It is impossible to determine the significance of such results, therefore abnormalities will not be shared with study participants because the meaning of the exam is not yet proven and is of unknown clinical benefit.

**6. Do any of the procedures listed above, under question # 2, utilize any imaging procedures for RESEARCH PURPOSES?**

**Examples:** ultrasound, CT scans/ x-rays etc.

**Answer/Response:** Yes.

**IF YES, list procedures:**

**Answer/Response:**

Non-radiating Electrical Impedance Tomography (EIT)

▶ IF YES, check one of the following two options:

This imaging research examination utilizes the same imaging techniques, equipment, scanning sequences that would be used if the subject were to have the imaging performed for clinical care. There exists the potential for the discovery of clinically significant incidental findings.

▶ If checked, answer the following:

**Will the images be read by a licensed radiologist and the reading placed in the subject's medical record?**

**Answer/Response:**

▶ IF NO: The PI takes full responsibility for the identification of incidental findings:

- The PI will have all incidental findings reviewed by a radiologist who will advise the PI regarding clinical significance.
- The PI will inform the subjects verbally of all incidental findings that are of clinical significance or are of questionable significance.
- A follow-up letter describing the finding should be provided to the subject with instructions to either show the letter to their PC or if the subject has no PCP, the subject should be instructed to make an appointment at UVA or at the Free Clinic.

This imaging research examination utilizes non-standard/investigational imaging modality, techniques, equipment, scanning sequences, etc. It is impossible to determine the significance of such images, therefore abnormalities will not be shared with the subject because the meaning of the exam is not yet proven and is of unknown clinical benefit.

**7. Will you be using viable embryos?**

IF YES, attach approval from UVA ESCRO Committee

**Answer/Response:** No

**8. Will you be using embryonic stem cells?**

IF YES, attach approval from UVA ESCRO Committee

Answer/Response: No

**9 Are any aspects of the study kept secret from the participants?**

Answer/Response: No

► IF YES, describe:

Answer/Response:

**10. Is any deception used in the study?**

Answer/Response: No

► IF YES, describe:

**INSTRUCTIONS:** Describe the deception involved and the debrief procedures. Attach a post-experiment debriefing statement and consent form offering participants the option of having data destroyed.

Answer/Response:

**11. If this protocol involves study treatment, explain how a subject will be transitioned from study treatment when they have completed their participation in the study.**

**Example:** If the subject will be taking an investigational drug, will they need to be put back on an approved drug when they have completed the study? If yes, explain how this will be accomplished and who will cover the cost. If the subject has a device implanted will it be removed? Again- who will cover the cost of the removal?

**Instructions:** Answer NA if this study does not involve a study treatment.

Answer/Response: N/A

**12. Will your study involve measures (C-SSRS/BID/SCID etc.) used to assess for depression and/or suicidality for research purposes? No**

**Answer this question YES if any of the following apply:**

- 1) The protocol has a research purpose to study suicide, suicidal ideation, depression or trauma
- 2) The protocol has a research purpose to study traumatic life events that may evoke powerful emotion or induce mood changes in participants;
- 3) The protocol includes **assessments** (e.g. Surveys, exams, questionnaires, etc.) that can be used to identify **depression and/or suicidal ideation** (thoughts of suicide, either active or passive), plan (the means or mechanism) or intent (the expressed desire and willingness to act on the plan).

**IF YES:**

- a. Which research staff members are qualified to assess suicidality/depression and will be available to provide care and intervention?

**Answer/Response:**

- b. Include specific guidelines for intervention based on assessment tools and rating scales. (i.e. based on C-SSRS/BID, SCID score of xxx, subject will be assessed further by the PI for suicide risk or referred urgently to an ED, crisis center, or clinic immediately).

**Answer/Response:**

- c. Describe a plan to link participants to psychological help if needed and include written materials listing those resources as an attachment to the protocol. This plan should include details of the planned interventions for differing severities of depression or suicidality, including a plan for how imminent risk of harm will be handled for the study's targeted population. (May include a list of local psychiatry/psychotherapy providers at UVA). **Note: If the subject is a patient at UVA Medical Center, you must adhere to Medical Center Policy 0140 Judicial Treatment Order and 0197 Suicide Risk Assessment and Prevention.**

